6.3 On-treatment Study Procedures

Table 6-1 Study calendar

Procedure	Footnotes	Screen Phase	Cycle 1					Cycle 2					Additional Cycles ¹³			Extended Access Phase	Safety Follow-up Phase
			Day 1	Day 2	Day 3	Day 8	Day 15	Day 1	Day 3	Day 8	Day 15	Day 1	Day 8	Day 15			
Informed consent		X														X	
Laboratory																	
CBC with differential; Coagulation parameters	1	X	X	X	X	X	X	X	X	X	X	X	X	X	X		
Chemistry	1	X	X	X	X	X	X	X	X	X	X	X	X	X	X		
Pregnancy	2	X	X														
Hepatitis	1	X															
B and T lymphocyte subsets	3		X					X	X			X					
Immunogenicity	4		X					X				X					
Pharmacokinetics	5		X			X		X				X					
Biomarkers	6		X	X	X	X	X	X	X	X	X						
Study Agent Admin																	
Sorafenib	7							Twice daily					X				
Mapatumumab/Placebo	7		X					X				X			X		
Physical/Clinical																	
Med Hx / Phys.Exam	-	X															
Vital signs	8	X	X			X	X	X		X	X	X			X		
Body weight	9	X	X					X				X					
Performance Status	10	X	X					X				X					
Record AEs/	11	X											<-----Throughout the study----->				

Table 6-1 Study calendar

Procedure	Footnotes	Screen Phase	Cycle 1				Cycle 2				Additional Cycles ¹³			Extended Access Phase	Safety Follow-up Phase
			Day 1	Day 2	Day 3	Day 8	Day 15	Day 1	Day 3	Day 8	Day 15	Day 1	Day 8	Day 15	
Conmeds															
Disease Assessments	12	X	Performed at the end of every 2 cycles (ie, Cycles 2, 4, 6) and every 2 cycles thereafter until radiologic PD is documented.										X		
α – Fetoprotein (AFP)	12	X	Performed at the end of every 2 cycles (ie Cycles 2, 4, 6) and every 2 cycles thereafter until radiographic PD is documented.												
ECG	-	X	Repeat as clinically indicated												

AE = adverse event; CBC = complete blood count; CT = computerized tomography; ECG = electrocardiogram; PD = progressive disease.

- ¹ Safety Labs: Day 1 (complete blood count with differential, coagulation parameters [INR, PT, PTT] and chemistry) must be performed within 3 days prior to dosing on Day 1 of each cycle. See [Appendix 7](#) for a detailed list of required laboratory assessments.
- ² Pregnancy: Serum test at screening, urine test pre-dose Cycle 1 Day 1; must be negative to receive treatment.
- ³ B and T lymphocyte subsets: Blood samples for quantification of B and T lymphocytes will be obtained in Cycles 1 and 2 only. Samples will be obtained on Day 1 (prior to dosing) and Day 15 of Cycles 1 and 2.

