- ¹¹ Adverse Events: (S)AE collection begins with the start of 1st study agent administration. Concurrent medications will be recorded within 28 days prior to Cycle 1 Day 1. For subjects in the Extended Access Phase, only SAEs will be recorded.
- ¹² Disease and α – Fetoprotein (AFP) Assessments: Radiologic and AFP assessments will be performed at the end of every 2 cycles (ie, Cycles 2, 4, 6, etc). For subjects discontinuing treatment prior to documentation of radiologic disease progression, disease assessments will be performed every 6 weeks (\pm 3 days), starting 6 weeks after the previous disease assessment while on study, until radiologic disease progression is documented. If disease progression is based only on new lesions or is equivocal, images will be provided to the blinded, independent reader for confirmation of disease progression. All imaging scans used for disease assessments will be made available for independent radiology review by the Sponsor or designee. For subjects in the Extended Access Phase, disease assessments will be performed as at least every 3 months or as per standard of care, whichever is sooner, until disease progression is documented. Independent radiological review of response or for confirmation of disease progression is not required.
- ¹³ Subjects who discontinue mapatumumab/placebo will complete the current cycle assessments per the study calendar. Subsequently, for subjects in the Extended Access Phase, subjects receiving sorafenib alone will be assessed as per local standard of care and will return at least every 6 weeks for BP monitoring. Serious adverse events will be recorded throughout the study

(concluded)

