6.8 Disease Response Assessments

Imaging endpoints will be determined using the modified RECIST criteria for HCC proposed by [Lencioni](#) 2010 mRECIST for HCC is a joint guideline of the American Association for the Study of Liver Diseases and the Journal of the National Cancer Institute.

Lesions which manifest typical imaging characteristics for HCC demonstrate intratumoral arterial contrast on CT and MRI images. mRECIST accounts for newer therapies which may impact tumor vascularity and may not yield a typical cytotoxic decrease in tumor size by incorporating changes in vascularity into the criteria for target lesion response. Diligence in obtaining images during the hepatic arterial contrast enhancement phase is a requirement at baseline and all subsequent scans. The same imaging method must be used at baseline and during follow up.

As in conventional RECIST, overall response is the result of the combined assessment of target, nontarget, and new lesions. There are also specifications for incorporating portal vein thrombosis, portal hepatic lymph nodes, and pleural effusions/ascites into the response assessment. As with conventional RECIST, the appearance of any new lesion overrides any existing lesion response, resulting in classification as progressive disease (PD). Key aspects of mRECIST as adapted for this study are summarized in [Appendix 4](#).

Baseline images will be provided to the BICR for confirmation of radiologic eligibility (measurable disease). Confirmation of radiologic eligibility for the study will be provided to the site by the BICR within 72 hours of receipt of images and will be required for randomization.

Disease assessments and an assessment of α -fetoprotein will be performed at the end of every 2 cycles (ie, Cycles 2, 4, 6 and every 2 cycles thereafter). The response assessment will be performed and documented no more than 5 days before the start of the next cycle. All images will be provided to the BICR following each disease assessment.

If disease progression is based only on new lesions or is equivocal, images will be provided to the BICR for confirmation of radiologic disease progression prior to discontinuing study treatment. PR and CR will be confirmed at the next scheduled disease assessment (no fewer than 4 weeks after the initial documentation of PR or CR).

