Stable Disease (SD): Any cases that do not qualify for CR, PR or PD.

Progressive Disease (PD): An increase of at least 20% in the sum of the diameters of viable (enhancing) target lesions, taking as reference the smallest sum of the diameters of viable (enhancing) target lesions recorded since treatment started.

Evaluation of nontarget lesions:

Complete Response (CR): Disappearance of intratumoral arterial enhancement.

Incomplete Response/Stable Disease (IR/SD): Persistence of intratumoral arterial enhancement in 1 or more nontarget lesions.

Progressive Disease (PD): Unequivocal progression of existing nontarget lesions.

Evaluation of new lesions: A newly detected hepatic nodule will be classified as evidence of progression when its longest diameter is ≥ 1 cm and the nodule shows the hypervascularization in the arterial phase with washout in the portal venous or late venous phase.

Liver lesions ≥ 1 cm that do not show a typical vascular pattern can be diagnosed as HCC by evidence of at least a 1 cm-interval growth in subsequent scans.

An individual radiologic event will be adjudicated in retrospect as progression at the time it was 1st detected by imaging techniques, even if strict criteria were fulfilled only on subsequent radiologic testing.

Images by another modality may be obtained, as clinically indicated post-baseline. Sites may conclude that post-baseline images based on another modality that indicate disease are evidence of radiologic progression if: (1) there was no imaging done at baseline; (2) if there was imaging done at baseline showing no disease present at that time; or (3) if there was imaging done at baseline indicating that the on-treatment assessment represents unequivocal worsening. In these cases the disease will be reported as 'new lesions'.

All images obtained on study will be provided the BICR for the independent efficacy read, or for confirmation of progression if required or requested.

Evaluation of Overall Response: The overall response is determined at each assessment and is a result of the combined assessment of target lesions, nontarget lesions and new lesions.

Overall Response Assessment

Target Lesions	Nontarget Lesions	New Lesions	Overall Response*
CR	CR	No	CR
CR	IR/SD	No	PR
PR	Non-PD	No	PR
SD	Non-PD	No	SD
PD	Any	Yes or no	PD
Any	PD	Yes or no	PD
Any	Any	Yes	PD

*AFP is not included in assessment of overall response.

Best Overall Response:

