The study is estimated to occur over approximately 24 months. Subjects will continue to receive sorafenib and/or mapatumumab/placebo until radiologic disease progression or unacceptable toxicity. Subjects may discontinue either sorafenib or mapatumumab/placebo separately and remain on treatment. After discontinuation of treatment, subjects will continue to be followed for radiologic disease assessments every 6 weeks (\pm 3 days), starting 6 weeks after the previous disease assessment while on treatment, until documented radiologic disease progression (if not previously documented). Thereafter, subjects will be followed every 3 months for survival until at least 90% of subjects have met the survival endpoint.

If disease progression is based only on a new lesion(s) or is equivocal, images will be provided to the BICR for confirmation of radiologic disease progression prior to discontinuing study treatment. Decisions regarding subject treatment will remain the responsibility of the investigator. Additionally, all images obtained on study will be provided to the BICR for the independent efficacy read.

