6.5 Concomitant Medications

Concomitant medications will be coded according to drug name as defined in the World Health Organization (WHO) Drug Dictionary, classified according to the Anatomical Therapeutic Chemical (ATC) classification system and presented in tables and listings.

7 Efficacy Analyses

Efficacy analyses will be based on the BICR assessment. Evaluation of efficacy endpoints based on investigator data will be provided by applying modified Response Evaluation Criteria in Solid Tumors for hepatocellular carcinoma (mRECIST for HCC) (Lencioni, 2010 and Llovet, 2008) to investigator assessed tumor measurements. In addition, investigator reported objective response and disease control rates will be summarized with the caveat that these may differ from the application of mRECIST for HCC to the investigator assessed tumor measurements. Investigator reported disease progression dates will be presented in listings but not analyzed using time to event analysis techniques. Instead these analyses will be performed on time to progression (TTP) and progression free survival (PFS) dates resulting from application of mRECIST for HCC to investigator assessed tumor measurements along with the censoring guidelines and missing data rules described in this Analytical Plan.

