7.1 Primary Efficacy Endpoint Analyses

7.1.1 Primary Efficacy Endpoint(s)

The primary endpoint is TTP defined as the time from randomization to radiologic disease progression based on BICR assessments of imaging scans using mRECIST for HCC (Llovet, et al, 2008 and Thomas, et al, 2010).

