7.3.2 Other Censoring Rules

Subjects who reach the survival endpoint due to any reason prior to experiencing a radiologic disease progression will be censored for TTP at the date of their last complete disease assessment. Subjects remaining on study without radiologic disease progression or death at the time of analysis will be censored for TTP and PFS at the date of their last

complete disease assessment. Subjects lost to follow-up prior to experiencing a radiologic disease progression or death will be censored for TTP and PFS at the date of their last complete disease assessment.

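### Could a site progression call end imaging without central confirmation, and so distort the BICR-based TTP and PFS?

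*Protocol*

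**What the plan says.** Both imaging endpoints rest on the central read. SAP 7.1.1 states: "The primary endpoint is TTP defined as the time from randomization to radiologic disease progression based on BICR assessments of imaging scans". SAP 7.2.1 puts the secondary endpoints, including PFS, on the same basis.

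The documents say when scanning stops but not on whose reading. The disease-assessment row of Protocol Table 6-1 (Section 6.3) runs "every 2 cycles thereafter until radiologic PD is documented". Footnote 12 covers subjects who leave treatment early, with six-weekly scans "starting 6 weeks after the previous disease assessment while on study, until radiologic disease progression is documented". SAP Sections 4 and 6.3 are equally silent on the reader. Only for Extended Access do footnote 12 and Protocol 6.8.1 waive independent review, which implies the local read there.

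Protocol 6.8 asks for central confirmation before treatment is stopped in two situations: "If disease progression is based only on new lesions or is equivocal, images will be provided to the BICR for confirmation of radiologic disease progression". All images go to the BICR in any case, and Appendix 5 also allows them to be sent "or for confirmation of progression if required or requested". SAP Section 4 adds: "Decisions regarding subject treatment will remain the responsibility of the investigator".

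On censoring, SAP 7.3.2 says: "Subjects remaining on study without radiologic disease progression or death at the time of analysis will be censored for TTP and PFS", with the date set at the last complete assessment. On the site's own calls, SAP Section 7 says: "Investigator reported disease progression dates will be presented in listings but not analyzed using time to event analysis techniques". SAP 7.1.3 nevertheless plans two TTP analyses that apply mRECIST to the investigator's measurements, and SAP 7.2.2 repeats them for PFS.

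**The concern.** Suppose the investigator's call counts as documentation. A clear target or non-target progression at the site then ends scanning with no mandatory central check. If the BICR later disagrees, no further scans exist on which it could find progression. The subject is censored for TTP just when the site judged the disease to be worse, and for PFS has an event only at death. Such censoring may be informative. It removes events from the primary test and, if the site was right, raises the BICR Kaplan-Meier medians. That would touch SAP 4.1, which reads the control arm against historical outcomes. If it happened more often in one arm, the hazard ratio would shift. No planned table classifies site-versus-BICR disagreement by arm.

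**Working it through.** **1. The plan's own figure.** Inputs (Protocol 9.2, SAP 5.1): medians 5.5 and 8.9 months, one-sided alpha 0.10, power 80%, 50 per arm.

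- HR = 5.5/8.9 = 0.618 under exponential times; ln HR = -0.481.
- Schoenfeld events = 4(1.282 + 0.842)²/0.481² ≈ 78. Power at 78 events is 0.801, so the stated 80% reproduces.
- The stated precision agrees. Solving median × exp(±1.96/√d) for -1.9 and +2.6 months gives a median of 7.06 and d = 39 per arm, or 78 in total.

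**2. Cost of equal discordance.** The documents give no discordance rate. Assume half of progressions are clear calls outside the confirmation rule and 10, 20 or 30% of those go unconfirmed. The overall share is then s = 5, 10 or 15%. The simulation used 20,000 trials per scenario, exponential TTP, 42-day scans, 12-month uniform entry and a one-sided log-rank test at 0.10. Analysis was either at 24 months or at the 90th site progression (90% of 100, SAP Section 3).

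| s | Events, 24 months | Power | Events, lock at 90 | Power, simulated | Power, Schoenfeld |
|---|---|---|---|---|---|
| 0 | 80.3 | 0.804 | 90 | 0.839 | 0.842 |
| 5% | 76.3 | 0.787 | 85.5 | 0.824 | 0.827 |
| 10% | 72.3 | 0.769 | 81.0 | 0.805 | 0.812 |
| 15% | 68.3 | 0.749 | 76.5 | 0.783 | 0.795 |

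At a harsher s = 30%, Schoenfeld power is 0.69 from a base of 78 events (54.6 left) and 0.735 from 90 (63 left).

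**3. Hazard ratio and type I error.** With equal s of 0, 5, 10 and 15%, null rejection is 0.102, 0.101, 0.102 and 0.101, and the large-sample Cox HR is 0.610, 0.613, 0.613 and 0.611. Equal discordance costs events and introduces no material bias in the comparison.

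Unequal s matters. Under the null the apparent HR is about (1 - s for mapatumumab)/(1 - s for control). For 7.5% control against 12.5% mapatumumab this is 0.875/0.925 = 0.946, and simulated rejection is 0.156; the reverse gives 0.062. At 10% against 20% the HR is 0.90/0.80 inverted, that is 0.80/0.90 = 0.889, and rejection is 0.22 by formula and 0.24 by simulation. The result follows the split that is assumed.

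**4. Control median.** With continuous assessment and true site calls, the median becomes 5.5/(1 - s) = 5.8, 6.1 or 6.5 months, a rise of 0.3, 0.6 or 1.0. With 42-day scans the simulated mean goes from about 6.2 (the scan grid alone) to about 6.5, 7.0 and 7.4, a rise of 0.3 to 1.2. All are smaller than the plan's -1.9 to +2.6 months. If unconfirmed calls are false positives unrelated to prognosis, the median is not biased upward at all.

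**5. What the planned analyses already capture.** SAP 7.1.3 applies mRECIST to site measurements. Under SAP 7.5, progression there is dated from target measurements, non-target responses or new lesions. A clear target or non-target site progression is therefore an event whether or not the BICR agrees. The natural extra analysis would keep BICR events and add unconfirmed site progressions at the site date. In the model of step 2 every site progression is either confirmed at that scan or added back there, so its data set is identical to the investigator-measurement analysis. It returns null rejection to 0.102 in both unequal scenarios, and in this model the planned analysis does the same.

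**The case for a change.** The best case for a change is that it is cheap. One supportive analysis and one by-arm table would use reads and dates already collected and need no scans. A five-point arm difference moves a nominal 0.10 test to about 0.16, and nothing planned counts that difference directly. The investigator analyses replace the central read for every subject and are derived from measurements, so they are not the site call that ended imaging.

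Part of this stands. The main-phase documents do not name the reader, and discordance is not tabulated. Outside the simplified model, where the BICR may also see progression that the site missed or date it differently, the two analyses would not coincide exactly.

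The rest is weaker. The view that the site call ends imaging leans on the investigator's authority over treatment, which is not authority over scanning; footnote 12 keeps scans going after treatment stops. The move to survival follow-up is triggered by the same open phrase, so it cannot settle the meaning. The 0.16 comes from a chosen imbalance. Site readers are blinded, as is the BICR, and no reason is offered why they should disagree more in one arm. Event counts by arm from the BICR and investigator analyses would show net disagreement, and the listed site dates allow a hand count. The added analysis would also create false events wherever the BICR was right.

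**Conclusion.** No change to the plan is needed. The silence on whose progression ends imaging is real, but it is confined to the main phase and leaves the primary result intact under the expectation that blinding supports. With 5 to 15% of progressions unconfirmed equally by arm, power is 0.75 to 0.79 at a 24-month cut-off, or 0.78 to 0.82 at 90 site progressions. Type I error stays at 0.10, the hazard ratio at about 0.61, and the shift in the control median is inside the stated precision. If documentation means the BICR's, the issue disappears.

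This rests on assumed discordance rates, exponential times, site calls treated as true progression, and no systematic arm difference. A much higher rate would cost more power (0.69 to 0.735 at 30%), and a systematic arm difference would bias the test; nothing in the documents points to either. The planned investigator-measurement TTP and PFS are the appropriate cross-check. Stating whose read ends imaging and counts toward the lock trigger, or adding a discordance table, would be optional clarification.

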6.8.1 Disease Response Assessments for Subjects in the Extended Access Phase

During the Extended Access phase, subjects will have regular visits for disease assessments at least every 3 months or as per standard of care, whichever is sooner, until disease progression is documented. Independent radiological review for confirmation of disease progression is not required.

AM03
15Jul15

6.9 Treatment after the end of the Study

The investigator is responsible for ensuring that consideration has been given to the post-study care of the subject's medical condition, whether or not GSK is providing specific post-study treatment

AM03
15Jul15

7 Pharmacokinetic, Immunogenicity, Pharmacodynamic and Exploratory Assessments

7.1 Pharmacokinetic Assessments

For determination of mapatumumab concentration, serum samples will be collected as outlined in [Table 6-1](#).

A manual will be provided regarding how to obtain blood samples, process samples, collect serum from the blood samples, and how to store and ship the serum samples. Bioanalysis will be carried out at Human Genome Sciences to determine mapatumumab concentration in each serum sample.

7.2 Immunogenicity

Blood samples for serum antibodies to mapatumumab will be obtained as outlined in [Table 6-1](#).

7.3 Pharmacodynamic Assessments

Subjects will be given the option to participate in an exploratory biomarker research sub-study. Consenting subjects will be asked to provide a historically obtained biopsy sample, if available, and blood samples. In addition, samples will be requested from subjects who undergo a biopsy during the treatment period.

To examine and quantify biomarkers present peripherally, blood will be drawn during Cycles 1 and 2, from which DNA and serum proteins will be isolated. The parameters evaluated may include, but may not be limited to, M30, TNF α , sTRAIL, soluble Fas ligand, interferon- α , interferon- γ , interleukin-2, interleukin-6, interleukin-8, interleukin-10, interleukin-12, and FC gamma receptor and interleukin-6 gene polymorphisms. The biomarker sub-study is detailed in [Appendix 6](#).

7.4 Exploratory Assessments (B and T Lymphocyte Subsets)

7.4.1 Rationale for B and T Lymphocyte Analysis

Over 400 subjects have received mapatumumab in doses ranging from 0.01 to 30 mg/kg across multiple Phase 1 and Phase 2 clinical trials in subjects with solid and hematologic malignancies. While there is no evidence to date that mapatumumab exacerbates adverse events associated with chemotherapy, the most commonly observed laboratory abnormality associated with mapatumumab has been lymphopenia. The lymphopenia has been intermittent and reversible and was not associated with infectious events. However, the lymphocyte subpopulation(s) affected have not been characterized.

The evaluation of lymphocytes will include complete blood count/differential and lymphocyte subpopulation analysis (numbers and percentages of T and B cells) by flow cytometry at a central laboratory. Blood samples will be examined by flow cytometry for levels of T helper (CD4+), T cytotoxic (CD8+) and mature B cells (CD19+).

